health care to meet the demands of diabetic care. With the widespread adoption of technology services nowadays, application of mobile app and wireless sensors, including the text, multimedia messaging and patients' SMBG, was proven to be effective in enhancing health outcome, such as medication adherence, HbA1C and self-managements [9-13]. However, there had been no previous study developed diabetes educational program based on the social media with two-way communication.

Objectives

This study developed an educational program, Taipei Medical University-Line Oriented Video Education (TMU-LOVE), based on the AADE7™. The social media employed in the study was LINE (©LINE Corporation limited, Japan). It was one of the most popular and user friendly social media platform in Taiwan, with high acceptance up to 91.5% among the population above 50 [14]. The study aims were: (1) to evaluate the effectiveness of TMU-LOVE on A1C, knowledge, attitudes and self-care activities by observing the changes before and after intervention; (2) to study the impact of TMU-LOVE on change of knowledge for diabetes patient with high or low levels of health literacy; (3) to explore the association between diabetes patients' attitudes and self-care activities.

Design and methods

This randomized controlled trial (RCT) was carried out from July 2020 to Jan 2021. The study was conducted in the Endocrinology and Metabolism Clinic in Wan-Fang Hospital. Participants were randomly divided into either control or intervention

groups. The control group received usual care while the intervention group received usual care and TMU-LOVE health education. Data were collected at baseline and 12 weeks after enrollment. The study was approved by the Taipei Medical University Jointed Institutional Review Boards (TMU-JIRB No.: N201905088).

Inclusion Criteria

The patient met the following criteria were included if they

- (1) Type 2 DM
- (2) Age 20 or older
- (3) Had at least 1 HbA1C data in the past 6 months
- (4) Possessed a smart-cellphone
- (5) HbA1C $\geq 6\%$

Exclusion Criteria

The patients were excluded if they had:

- (1) Gestational diabetes
- (2) Cognitive impairment
- (3) No medication treatment but dietary control alone

Control Group

Patients in the control group received usual health care, including outpatient services with physicians, nurses and pharmacists. The consultation by certified diabetes educators (CDE) was referred by physicians as needed.

Intervention Group

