In addition to usual health care, patients in the intervention group were asked to join

the TMU-LOVE education platform.

Sample Size Calculation

The sample size of this study was estimated using G-power (version 3.1, Heinrich-Heine-Universität Düsseldorf, Germany). Assuming a power of 80% with a two-sided alpha level for detecting the difference between the intervention group and the control group, at least 64 patients were needed for each group. Considering a 20% dropout rate, the study was designed to have at least 80 patients for each group, 160 patients in total.

Randomization

Patients were randomized in a 1:1 ratio according to the random allocation sequence generated prior to the study. Patients with odd numbers were allocated to the control group while even numbers were allocated to the intervention group. The trial was non-blinded because of its feasibility.

Program description

With advantages of social-media integration, TMU-LOVE was conducted as a platform using LINE. It allowed for a one-on-one chat room, graphic messages, and the ability to steer customers to certain websites [15]. The study created a graphic menu which was composed of six parts, including understanding diabetes, daily care, nutrition care, diabetes drugs, quizzes, and questions and answers (Q&A). Patients could click on the menu for corresponding information. The messaging feature of TMU-LOVE also allowed researchers to send educational videos and communicate with patients by text message, or voice or video call. Patients could ask questions, and the research team would response with a suitable explanation via TMU-LOVE.

The content of TMU-LOVE included 51 diabetes educational videos according

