to the seven key points in AADE7™ [2]. The videos were produced by undergraduate students in the School of Pharmacy, Taipei Medical University (TMU) and then verified by two pharmacists. Each video lasted 2~3 minutes, and videos were divided into five categories: 10 on understanding diabetes, 10 on daily care, six on nutrition care, 21 on diabetes drugs and four on diabetes knowledge-related quizzes. There were 21 diabetes drug videos based on the formulary at Wan Fang Hospital, including metformin, acarbose, dipeptidyl peptidase-IV (DPP-IV) inhibitors, meglitinide, sulfonylurea, thiazolidinedione, sodium-glucose cotransporter-2 (SGLT2) inhibitors, and insulin. All of the videos are listed in Multimedia appendices 1 and are also available at the website of the TMU School of Pharmacy [16].

The program was designed for a 12 week duration, with two or three videos sent every week and a care message sent every 2 weeks to patients in the intervention group. All patients received the same videos except those for medications. Videos regarding a basic understanding of diabetes were arranged firstly in weeks 1~4. Those for daily care were begun from week 5, with six nutrition care videos scheduled in 6 different weeks. Each patient received the videos for their individual medications in weeks 4, 6, 7, 11, and 12. There were four quizzes scheduled in weeks 3, 6, 9, and 12. Patients could also access to all videos through TMU-LOVE whenever they wanted.

Data collection

Questionnaire assessments in this study included A1C, patients' knowledge about diabetes, self-care activities, attitudes towards diabetes and health literacy. All data would be assessed at baseline and 12 weeks after enrollment except for health literacy. Questionnaire utilized in this study composed of 5 parts, including personal information, Simplified True / False version of Diabetes Knowledge Scale (SDKS) [18], Summary of Diabetes Self Care Activities (SDSCA) [20], Diabetes Care Profile-

Attitudes Toward Diabetes Scales (DCP-ATDS) [18] and Newest Vital Sign (NVS) [23].

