Patients' knowledge about diabetes was measured by True / False version of SDKS. It contained 24 items and was validated in previous studies [17,18]. The measurement of patients' self-care activity was done by using SDSCA, which consisted of 10 items. It asked patients how many days per week did they had performed the right behavior regarding to medication adherence, diet, exercise, self-monitoring blood glucose and foot care. Its validity was proven in previous studies [19, 20]. Patients' attitude towards diabetes was assessed by questionnaire DCP-ATDS, which was previously validated and translated [18, 21]. It contained 17 items which could be divided into positive attitude, negative attitude, self-care ability, self-care adherence and importance of care. Each item was five-point Likert scale as graded for strongly agree, agree, neutral, disagree and strongly disagree. For assessment of health literacy, we used NVS, which was developed and translated in previous studies [22, 23]. It consisted of 6 questions designed based on an ice-cream nutrition label to evaluate both the reading and numeracy level of patients.

Statistical analysis

Statistical analyses were conducted using SPSS (SPSS, Released 2009. PASW Statistics for Windows, ver. 28.0. Chicago, IL, USA). The study was performed by intention-to-treat analysis. Multiple imputation was employed to manage the missing values. All tests were two-tailed, with a significance level of 0.05. Differences in baseline characteristics were examined using descriptive analysis. The Kolmogorov-Smirnov (KM) test was used to verify whether the variables had normal distributions. According to the results of KM test, a Wilcoxon signed rank test or paired t-tests were

used to examine the differences in the pretest and post-test scores within a group, while a Mann-Whitney test or unpaired t-tests were performed to compare the differences between groups. An ordinal logistic regression model was applied to evaluate the association of health literacy with knowledge, attitudes, and self-care activities.

References

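### The between-arm tests for Aim 1 ignore the baseline value as a covariate; a baseline-adjusted regression would be at least as precise as the planned t-test, at very little cost

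*Combined protocol and SAP*

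**What the plan says.** All references are to the combined protocol and SAP.

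- **Objectives.** Aim 1 is "to evaluate the effectiveness of TMU-LOVE on A1C, knowledge, attitudes and self-care activities by observing the changes before and after intervention".
- **Data collection.** "All data would be assessed at baseline and 12 weeks after enrollment except for health literacy". All four Aim 1 outcomes therefore have a baseline value.
- **Sample Size Calculation.** The trial is sized "for detecting the difference between the intervention group and the control group", at 64 per group, raised to 80 for 20% dropout. No effect size, SD or correlation is given.
- **Statistical analysis.** A Kolmogorov-Smirnov test chooses between parametric and rank tests. Between arms, "a Mann-Whitney test or unpaired t-tests were performed to compare the differences between groups". Paired tests are used within each arm. For baseline, "Differences in baseline characteristics were examined using descriptive analysis". For incomplete data, "Multiple imputation was employed to manage the missing values".

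The only regression named is an ordinal logistic model for health literacy, which is not described as an arm comparison. No analysis adjusts the arm comparison for the baseline value of the outcome.

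The plan does not say outright what is compared between arms. The wording of Aim 1, and the pretest and post-test differences named in the same sentence as the between-arm test, make change scores the natural reading. Week-12 scores remain possible.

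**The concern.** A baseline value of the same outcome is usually the strongest predictor of the week-12 value, and here it is already in hand. A t-test on week-12 scores discards it. A t-test on change scores uses it, but fixes its coefficient at 1 whatever the data show. Regression on baseline estimates the coefficient. At stake is the width of the interval for the effect on A1C, knowledge, attitudes and self-care from the same patients. Validity and bias are not in question, because randomisation protects the unadjusted comparison.

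**Working it through.** **Inputs from the document.** 64 per arm, 20% dropout, 80 per arm, 160 in total, 80% power, two-sided (Sample Size Calculation); significance level 0.05 (Statistical analysis).

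**Assumed, because the document is silent.** Standardised difference d = 0.5; correlation r between baseline and week 12 of 0.3, 0.5, 0.6 or 0.7; k = SD at week 12 divided by SD at baseline, first set to 1; roughly normal data; 64 completers per arm standing in for 80 with 20% missing. The effect of imputation itself is not modelled.

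**1. The plan's own figure.** With d = 0.5 a two-sample t-test needs 64 per arm (power 80.1%; the normal approximation gives 63). With d = 0.4 it needs 100, and with d = 0.6 it needs 45. So 64 fits d = 0.5 but cannot be derived from the document alone. The dropout step reproduces: 64/(1 − 0.20) = 80, and 2 × 80 = 160.

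**2. Variance of the arm difference.** With baseline SD = 1, in units of 2/n:

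- week-12 score: k²
- change score: 1 + k² − 2rk
- regression on baseline: k²(1 − r²)

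Change minus regression is 1 − 2rk + r²k² = (1 − rk)². This is never negative, and is zero when rk = 1. Week-12 minus regression is k²r², also never negative. The regression is therefore at least as precise as either t-test in large samples at any SD ratio, apart from one degree of freedom.

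**3. Interval width at k = 1.** The large-sample ratios are √((1 + r)/2) against change and √(1 − r²) against week 12. Simulated ratios, which include the cost of estimating the slope, are:

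| r | regression/change | regression/week-12 |
|---|---|---|
| 0.3 | 0.810 (19% narrower) | 0.958 (4%) |
| 0.5 | 0.869 (13%) | 0.870 (13%) |
| 0.6 | 0.898 (10%) | 0.804 (20%) |
| 0.7 | 0.926 (7%) | 0.717 (28%) |

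At r = 0.9 the gain over change is 2%. At r = 0 the regression interval is 0.4% wider than for week-12 scores, and power is 79.8% against 80.1%. That is the full cost of the covariate.

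**4. Other SD ratios, regression against change.** At k = 1.2:

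- r = 0.5: √(1.44 × 0.75/1.24) = 0.933, 7% narrower
- r = 0.6: √(1.44 × 0.64/1.00) = 0.960, 4% narrower
- r = 0.7: √(1.44 × 0.51/0.76) = 0.983, 2% narrower

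At k = 1.25 and r = 0.8, rk = 1 and the gain is nil. Below 1 the gain grows: at k = 0.8 and r = 0.5, √(0.64 × 0.75/0.84) = 0.756, or 24% narrower.

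**5. Power at 64 per arm, k = 1.** The answer for the unadjusted tests depends on the scale of d, and both scales reproduce 64.

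| d = 0.5 in | analysis | r = 0.3 | 0.5 | 0.6 | 0.7 |
|---|---|---|---|---|---|
| week-12 SDs | change | 66% | 80% | 88% | 95% |
| | week-12 | 80% | 80% | 80% | 80% |
| | regression | 84% | 90% | 94% | 98% |
| change SDs | change | 80% | 80% | 80% | 80% |
| | week-12 | 91% | 80% | 71% | 58% |
| | regression | 94% | 90% | 88% | 86% |

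To match the regression with 64 completers, a change-score t-test needs 64 × 2/(1 + r), about 98/85/80/75 per arm.

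**6. Non-normal data.**

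- *Bounded score.* Of the knowledge scale the plan says "It contained 24 items and was validated in previous studies". A simulated 24-item score (SD 4.5, arm difference 2.2 points, r about 0.3/0.5/0.6/0.7) gives power of 66/79/86/95% for a t-test on change, 64/76/85/93% for Mann-Whitney on change, and 86/92/95/98% for the regression with robust standard errors. Type I error is 4.4 to 5.6% throughout.
- *Heavy tails.* With t residuals on 3 df and d in change SDs, Mann-Whitney on change against the robust regression gives 91 v 90% at r = 0.5, 92 v 90% at 0.6 and 93 v 87% at 0.7.
- *Skew.* With skewed residuals at r = 0.7 it gives 93 v 86%.

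**The case against.** The strongest reply is that nothing here is wrong. The planned tests hold their type I error, and the plan already has a remedy for non-normal data: it switches to Mann-Whitney, which can beat a linear model when residuals are heavy-tailed or skewed and r is about 0.6 or more. The document gives no distribution for any outcome, so this cannot be ruled out. This part of the objection stands, and it is why the Mann-Whitney test should be kept and reported beside the adjusted model.

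The equal-SD assumption also matters. Eligibility requires HbA1C of at least 6%, which truncates the baseline distribution, so k = 1 cannot be taken for granted. It would be wrong to say that change scores over-correct whenever r is below 1; they do so when rk is below 1. This too stands, and it widens the range of the possible gain in both directions.

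A reader might infer from the 66% entry in the power table that the trial is underpowered. The documents do not support that. They state no effect size or SD, and if d = 0.5 is in change-score SDs the change-score test has 80% power at every r. The 98/85/80/75 completers are what it takes to equal a better model, not what the trial needs.

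That change scores already use the baseline is true, but it does not remove the point. With equal SDs and r below 0.5 they are less precise than ignoring baseline altogether.

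**Conclusion.** The point holds as a low-cost gain in precision. The plan's only between-arm tests are unadjusted, and the covariate is collected for every Aim 1 outcome. Against a t-test on either score, the baseline-adjusted regression is at least as precise in large samples whatever the correlation and SD ratio, apart from one degree of freedom. The percentages rest on assumed r, equal SDs, near-normal data and 64 completers per arm.

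Three stronger readings should be resisted. The planned tests are not biased or invalid. The interval is not necessarily wider than it needs to be for all four outcomes: the gain over change scores is nil when r times the SD ratio is about 1, and there is none over week-12 scores when r is near 0. Nor is the regression generally superior to Mann-Whitney. Confidence is high in the principle and lower in the size of the gain for any one outcome.

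**What to change.** - For each Aim 1 outcome, estimate the between-arm effect by linear regression of the week-12 value on arm and the baseline value of the same outcome. Fit it in each imputed data set, pool, and report the adjusted difference with its 95% CI. Use robust standard errors if residuals are clearly non-normal.
- Keep the planned Mann-Whitney test, state that it is applied to change scores, and report it beside the adjusted model.
- Keep the within-arm tests as description only.
- On timing: "This randomized controlled trial (RCT) was carried out from July 2020 to Jan 2021", while the document is dated 10/02/2022. If results had already been seen, label the adjusted model as specified afterwards and set it beside the planned test.

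The cost is one paragraph of the analysis section and one degree of freedom per model, with no new data or patients. If the model has to be labelled as specified afterwards, it carries less weight as confirmatory evidence but is still worth reporting.

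### Aim 2 asks for the programme's effect on knowledge change by health literacy, but the only planned analysis using literacy names no arm, no change and no arm-by-literacy term

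*Combined protocol and SAP*

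**What the plan says.** The Objectives section of the combined protocol and SAP gives Aim 2 as "to study the impact of TMU-LOVE on change of knowledge for diabetes patient with high or low levels of health literacy" and Aim 3 as "to explore the association between diabetes patients' attitudes and self-care activities".

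The Statistical analysis section contains three inferential analyses:

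- paired tests of pre- and post-test scores within each group;
- between-group tests: "a Mann-Whitney test or unpaired t-tests were performed to compare the differences between groups";
- one regression: "An ordinal logistic regression model was applied to evaluate the association of health literacy with knowledge, attitudes, and self-care activities".

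Literacy appears only in the third. That section also says "Multiple imputation was employed to manage the missing values", without giving the imputation model.

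The Data collection section says that literacy is measured with the six-question Newest Vital Sign (NVS), and gives no cut-off between high and low. On timing it says "All data would be assessed at baseline and 12 weeks after enrollment except for health literacy", which leaves open when the NVS was taken.

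**The concern.** Aim 2 is a treatment effect at each of two literacy levels. The ordinal model, as described, asks whether literacy goes with knowledge. These are different questions. Literacy and knowledge can be related when the programme works equally well at both levels, and also when it does nothing. A benefit confined to low-literacy patients can narrow the knowledge gap between the levels and so make the association harder to detect. A reader given this association as the answer to Aim 2 could therefore be misled in either direction.

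A second, smaller gap concerns Aim 3. The model links attitudes and self-care each to literacy, and nothing in the plan links them to each other.

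**Working it through.** **1. Aims against analyses.**

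| Aim | What it needs | What the plan names |
|---|---|---|
| 2 | arm, change in knowledge, literacy level | literacy and knowledge; no arm, change, visit or interaction |
| 3 | attitudes with self-care | each with literacy; not with each other |

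The finding rests on this comparison. The figures below only show its size.

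**2. Inputs.** The Sample Size Calculation section gives 64 patients per group, raised to 80 for 20% dropout: 64/(1 − 0.20) = 80. It states no effect size. With an assumed 0.5 SD, two-sided 5% and 80% power, the t-test needs 63.8, so 64 reproduces under that assumption. It is the size for the overall arm comparison. I use 2 × 64 = 128 evaluable patients.

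The other inputs are assumptions: normally distributed literacy and knowledge, correlation 0.6 between baseline and week-12 knowledge, 0.4 between literacy and baseline knowledge, and ρ = 0.24 or 0.4 between literacy and week-12 knowledge before any treatment effect. High-literacy share is 30%, 50% or 70%.

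**3. Simulated rejection rates** (2000 trials per cell, 5% level, two literacy levels, proportional-odds score test for the association).

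| Test | No effect | Equal 0.5 SD | 0.5 SD in low literacy only |
|---|---|---|---|
| Literacy with week-12 knowledge, ρ = 0.24 | 55–58% | 50–55% | 10–12% |
| Same, ρ = 0.4 | 94–97% | 93–96% | 59–62% |
| Literacy with change, no arm, ρ = 0.24 | 31–38% | not run | 83–89% |
| Same, ρ = 0.4 | 4–5% | not run | 28–33% |
| Arm by literacy, baseline-adjusted | about 5% | about 5% | 34–41% |

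Re-running the week-12 association with other tests (correlation, Mann-Whitney) moved the figures by at most about 4 points.

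**4. Hand check at an even split.** The mean gap in week-12 knowledge between the levels is 2ρ√(2/π) = 1.596ρ. At ρ = 0.24 it is 0.383 SD. The within-level SD is √(1 − 0.24² × 2/π) = 0.981 and the SE is 0.981 × √(1/64 + 1/64) = 0.174. Then z = 0.383/0.174 = 2.2, and power is Φ(2.2 − 1.96), about 60%, slightly above the rank-based simulation. A 0.5 SD benefit to the treated half of the low-literacy patients cuts the gap by 0.25, to 0.133 SD. Then z is about 0.75 and power about 12%.

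**5. Precision of the analysis Aim 2 needs.** With baseline adjustment the residual SD is √(1 − 0.6²) = 0.8. For low-literacy share q and 64 per arm, SE(interaction) = 0.8 × √(2/(64q) + 2/(64(1 − q))).

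- q = 0.5: SE = 0.283; 95% CI ± 1.98 × 0.283 = ± 0.56 SD; power for 0.5 SD = Φ(0.5/0.283 − 1.96), about 42%.
- q = 0.3: SE = 0.309; 95% CI ± 0.61 SD; power about 37%. Simulation across the splits gives 34% to 42%.
- Arm effect within a level at an even split: ± 1.98 × 0.8 × √(2/32) = ± 0.40 SD.
- At an even split the interaction interval is ± 0.67 SD (power 31%) if the baseline correlation is 0.3, and ± 0.42 SD (power 65%) if it is 0.8.
- On an outcome with SD 1 and no baseline adjustment, power is 29% (q = 0.5) or 25% (q = 0.3).

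**6. Imputation.** With 160 patients, 20% of week-12 values missing at random and 10 imputations (500 trials), a true interaction of −0.50 is estimated as −0.39 when the imputation model omits arm by NVS, and as −0.49 when it includes it.

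**7. Ceiling.** Of the knowledge scale (SDKS) the plan says "It contained 24 items and was validated in previous studies". With an assumed SD of 4 and scores capped at 24, an equal 1.0 SD benefit makes the interaction test reject in 9% to 17% of trials at a mean of 20. With an equal 0.5 SD benefit it rejects in 5% to 7%. The ceiling is therefore worth checking, but is not a main issue.

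**The case against.** The section is brief about every analysis. It lists no covariates and does not say which variable is the ordinal outcome, so an arm term cannot be ruled out. Nor does it say that the ordinal model is meant to answer Aim 2. The between-group tests can be read as comparing change between arms; run within each literacy level, they would give the arm effects that Aim 2 literally asks for. The aim does not ask for an interaction test.

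The figures can also be challenged. Aim 2 is about change. On that reading, if literacy correlates equally with knowledge at both visits (0.4), the arm-free model rejects in only 4% to 5% of trials with no effect; the 31% to 38% needs the correlation to fall from 0.4 to 0.24. Finally, the trial was not sized for effects by literacy.

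Much of this stands as a limit on the claim. The harm is conditional on using the ordinal model for Aim 2, and its size depends on assumed correlations. But the plan does not say that any test is run by literacy level and sets no cut-off, so the by-level route is a possibility and not a plan. Separate tests at each level would also invite the inference that the effect differs whenever one is significant and the other is not, which only the interaction addresses. On the change reading, a model without arm still cannot separate a programme effect from change that would have happened anyway.

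**Conclusion.** The concern holds. As written, the plan leaves Aim 2 without an analysis based on the randomised comparison, and Aim 3 without any analysis. This follows from the text and needs no assumption.

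The size is illustrative. On week-12 scores, the association would be significant in roughly half to nearly all trials with no effect or an equal effect, for assumed correlations of 0.24 to 0.4. On change scores, the rate with no effect runs from about 5% to 38%, depending on whether the correlation is stable.

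This should be corrected, but it does not threaten the main result: the overall arm comparison in Aim 1 is unaffected. Aim 3 is worded as exploratory, so its gap weighs less.

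**What to change.** **Aim 2.**

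- Regress week-12 SDKS on arm, baseline SDKS, NVS level and arm by NVS level. Report the arm effect with 95% CI at each level and the interaction with its CI, labelled exploratory.
- Take the high/low cut-off from a source outside the trial data, and repeat with the NVS total score.
- Include arm by NVS in the multiple-imputation model.
- State when the NVS was taken; if it was not at baseline, report that as a limitation.
- The trial ran to January 2021 and the document is dated 2022. If results by literacy level had already been seen, label the analysis post hoc.
- Report the share at the top SDKS score by arm and level. If it is large, repeat with a Tobit model.
- Keep the ordinal model only as a description of what goes with literacy.

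**Aim 3.** Relate self-care (SDSCA) to attitudes (DCP-ATDS) at the same visit, with 95% CI, adjusting for arm at week 12. Of the attitude scale the plan says "It contained 17 items which could be divided into positive attitude, negative attitude, self-care ability, self-care adherence and importance of care". Report its self-care ability and self-care adherence parts separately, since they overlap in content with the SDSCA.

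**Cost.** Some added wording and two regressions on data already collected. The drawback is imprecision: an interaction interval of about ± 0.4 to ± 0.7 SD at an even split, for baseline correlations of 0.8 down to 0.3. Only large differences by literacy could be ruled out, and the report should say so.
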